Good documentation practices should be used on all study documentation. The clinical study will be performed in accordance with the protocol, applicable standard operating procedures (SOPs), the International Conference on Harmonization Good Clinical Practice (ICH GCP) guidelines, and applicable local regulatory requirements and laws.

The Sponsor requires that all records (e.g., ICFs, source documents, test article dispensing record, etc.) which support CRFs/source documentation of this study must be retained in the files of the responsible investigator for a period of 2 years from the time the final report is issued.

If the investigator relocates, retires, or for any reason withdraws from the trial, the Sponsor should be prospectively notified. The study records must be transferred to an acceptable designee, such as another investigator, another institution, or to the Sponsor. The investigator must obtain Sponsor's written permission before disposing of any records, even if retention requirements have been met. The Sponsor must be notified in writing of the name and address of the new custodian prior to re-assignment/transfer.

All records identifying the subject will be kept confidential and, to the extent permitted by the applicable laws and/or regulations, will not be made publicly available. Only the subject number will be recorded in the CRF. The code that links the subject to the subject's ID# is stored on paper in a locked cabinet, accessible only by Department of Dermatology research personnel. Photographs will be stored on the camera for approximately one week before being transferred to the computer database. Study findings stored on a password-protected computer will be encrypted and stored in accordance with local data protection laws. As part of the informed consent process, the subjects will be informed in writing that representatives of the IRB, or regulatory authorities may inspect their medical records to verify the information collected, and that all personal information made available for inspection will be handled in strictest confidence and in accordance with local data protection laws. If the results of the study are published, the subject's identity will remain confidential. Only the investigator will maintain a list to enable subjects to be identified. The data will be stored indefinitely.

d) Provisions to Monitor the Data to Ensure the Safety of Subjects

Part I: Elements of a Data and Safety Monitoring Plan

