This will be a single-center, randomized, double-blinded, vehicle-controlled clinical study to determine the efficacy of Enstilar® foam, a combination of calcipotriene and betamethasone dipropionate 0.005%/0.064%, in the treatment of psoriasis vulgaris in SOC (FST IV-VI). A total of 25 subjects (ages 18+, male and female, BSA ≥2%, PASI Score ≥ 2, IGA mod 2011 score ≥ 2) are expected to complete this study, which will run for a total of up to 12 weeks.

The study consists of three periods: Screening (from 0 to 4 weeks); Double-blind, vehicle-controlled treatment period (4 weeks), and open-label treatment period (4 weeks). During the second period (double-blind, vehicle-controlled), a total of 20 subjects will be randomized to Enstilar® and a total of 5 subjects will be randomized to vehicle. Those who meet all of the inclusion/exclusion criteria and are enrolled in the study will receive study drug (either Enstilar® or vehicle) for the entire treatment period.

1) Objectives

The purpose of this study is to evaluate the efficacy and safety of combination calcipotriene and betamethasone dipropionate 0.005%/0.064% foam in the treatment of psoriasis vulgaris in males and females with skin of color (SOC).

 Mount Sinai	Protocol Name:	A double-blinded, placebo-controlled study to evaluate the tolerability and efficacy of Enstilar® (calcipotriene and betamethasone dipropionate) Foam in the treatment of chronic plaque psoriasis in patients with skin of color (Fitzpatrick skin phototypes IV-VI).
	Principal Investigator:	[name], MPH
	Primary Contact Name/Contact Info:	[name], MPH [contact]
	Date Revised:	08/10/2017
	Study Number:	IF2166478

2) Background

Psoriasis is a chronic inflammatory disorder primarily affecting the skin and joints. This condition occurs in different ethnic groups worldwide with varying prevalence. In the United States, the Health and Nutrition Examination Survey estimated the prevalence of psoriasis to be 3.2% in adults; a significant number of affected were of darker phototypes, including African Americans (1.9%) and Hispanics (1.6%).^{1,2} The true prevalence of psoriasis in black and Hispanic populations may actually be higher, given that non-whites are more likely to have undiagnosed psoriasis than whites (in part due to barriers to care and decreased health care utilization in these groups).^{3,4}

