 Mount Sinai	Protocol Name:	A double-blinded, placebo-controlled study to evaluate the tolerability and efficacy of Enstilar® (calcipotriene and betamethasone dipropionate) Foam in the treatment of chronic plaque psoriasis in patients with skin of color (Fitzpatrick skin phototypes IV-VI).
	Principal Investigator:	[name], MPH
	Primary Contact Name/Contact Info:	[name], MPH [contact]
	Date Revised:	08/10/2017
	Study Number:	IF2166478

3. Ongoing use of other psoriasis treatment including but not limited to topical or systemic corticosteroids, other topical medications (i.e. coal tar), oral or biologic medications for the treatment of psoriasis, and UV therapy. The following washout periods will be required:
 - 2 weeks for topical therapy
 - 2 weeks for phototherapy
 - 12 weeks for biologic or targeted therapies
 - 4 weeks for other systemic therapies
4. Use of oral estrogen therapy, excluding oral contraceptive pills
5. Women who are pregnant, nursing, or of child-bearing potential who are unwilling to use appropriate method(s) of contraception.
6. Patients unwilling to limit exposure to UV light
7. Current significant medical problems that, in the discretion of the investigator, would put the patient at significant risk
8. Patients with disorders of calcium metabolism and/or hypercalcemia.
9. Use of any investigational drug within 4 weeks prior to randomization, or 5 pharmacokinetic/pharmacodynamics half-lives, if known (whichever is longer).
10. History of allergy to any component of the IP

c) Number of Subjects

Patients with skin types IV-VI with chronic plaque-type psoriasis will be screened with a goal of 25 total subjects randomized. All 25 randomized subjects are expected to complete all study procedures. Individuals who provide informed consent and fail to meet all of the inclusion and exclusion criteria during the initial evaluation will be considered a “screening failure.”

d) Study Timelines

The study will consist of 6 visits over up to 12 weeks (up to 4 week screening period plus 8 weeks enrolled in study). Study visits will be conducted at Screening (Visit 1), Baseline (Visit 2, Week 0), Week 1 (Visit 3), Week 2 (Visit 4), Week 4 (Visit 5), and Week 8/discontinuation (Visit 6).

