 Mount Sinai	Protocol Name:	A double-blinded, placebo-controlled study to evaluate the tolerability and efficacy of Enstilar® (calcipotriene and betamethasone dipropionate) Foam in the treatment of chronic plaque psoriasis in patients with skin of color (Fitzpatrick skin phototypes IV-VI).
	Principal Investigator:	[name], MPH
	Primary Contact Name/Contact Info:	[name], MPH [contact]
	Date Revised:	08/10/2017
	Study Number:	IF2166478

Enrollment will occur over a 6 month period from November 2017 to May 2018.

e) Endpoints

Primary Endpoint:

1. Investigator Global Assessment (IGA mod 2011) at week 4

Proportion of patients at week 4 who achieved treatment success according to investigator global assessment (IGA mod 2011) of the entire body including scalp. IGA will range from 0 (clear) to 4 (severe). Treatment success is defined as IGA of clear (0) or almost clear (1) for patients with \geq moderate disease at baseline or IGA of clear (0) for patients with mild disease at baseline.

Secondary Endpoints:

1. Psoriasis Area and Severity Index 50 and 75 (PASI50 and PASI75) at weeks 2, 4, and 8.

Proportion of patients achieving $\geq 50\%$ improvement and/or $\geq 75\%$ improvement in Psoriasis Area and Severity Index (PASI) at weeks 4 and 8 compared to baseline (PASI 50 and PASI 75, respectively). PASI will be completed by the investigator or trained qualified designee at screening and weeks 0, 2, 4, and 8.

2. Psoriasis Scalp Severity Index 50 and 75 (PSSI50 and PSSI75) at weeks 2, 4 and 8, if applicable

Proportion of patients achieving $\geq 50\%$ improvement and/or $\geq 75\%$ improvement in Psoriasis Scalp Severity Index (PSSI) at weeks 4 and 8 compared to baseline (PSSI 50 and PSSI 75, respectively), if applicable. PSSI will be completed by the investigator or trained qualified designee at screening and weeks 0, 2, 4, and 8 if the subject has/had scalp involvement at the baseline visit.

3. Investigator Global Assessment (IGA mod 2011) at weeks 2 and 8

Proportion of patients at week 8 who achieved treatment success according to investigator global assessment (IGA mod 2011) of the entire body including scalp. IGA will range from 0 (clear) to 4 (severe). Treatment success is defined as IGA of clear (0) or almost clear (1) for patients with \geq moderate disease at baseline or IGA of clear (0) for patients with mild disease at baseline.

4. Scalp Investigator Global Assessment (ScIGA) at weeks 4 and 8, if applicable

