Urine Pregnancy Test		X	X				
BSA		X	X		X	X	X
Investigator IGA mod 2011 score (and ScIGA if applicable)		X	X		X	X	X
PASI score (PSSI if applicable)		X	X		X	X	X
Mexameter measurement of erythema and melanin indices			X		X	X	X
Investigator dyspigmentation VAS			X			X	X
Patient Global Assessment of severity (PaGA)			X		X	X	X
Patient pruritus VAS			X	X	X	X	X
Patient dyspigmentation VAS			X			X	X
Dermatology Life Quality Index (DLQI)			X		X	X	X
Local Tolerability Assessment			X	X	X	X	X
Treatment satisfaction evaluation					X	X	X
Study Drug Training			X				
Study Drug Dispensation and Return			X			X	X

 Mount Sinai	Protocol Name:	A double-blinded, placebo-controlled study to evaluate the tolerability and efficacy of Enstilar® (calcipotriene and betamethasone dipropionate) Foam in the treatment of chronic plaque psoriasis in patients with skin of color (Fitzpatrick skin phototypes IV-VI).
	Principal Investigator:	[name], MPH
	Primary Contact Name/Contact Info:	[name], MPH [contact]
	Date Revised:	08/10/2017
	Study Number:	IF2166478

This is a single-center study and will consist of 3 phases. Phase 1 - screening phase, Phase 2 - Double-blinded, vehicle-controlled phase, and Phase 3 - Open-label and maintenance phase

Phase 1 - The screening phase will last up to 28 days. Screening and baseline may occur on the same day if subject does not require a wash-out period.

Phase 2 - double-blinded, placebo-controlled phase to evaluate the tolerability and efficacy of Enstilar® (calcipotriene and betamethasone dipropionate) Foam versus placebo in the treatment of chronic plaque psoriasis in patients with skin of color (Fitzpatrick skin phototypes IV-VI). This phase will last 4 weeks (baseline to week 4). Subjects will be randomized in a 4:1 ratio to Enstilar® or placebo, respectively. The study product will be applied once daily for 4 weeks.

Phase 3 - Open-label and maintenance phase. Subjects who were randomized to placebo during phase 2 will receive Enstilar daily x 4 weeks. Subjects who were randomized to Enstilar during phase 2 will switch to Enstilar twice weekly x 4 weeks as maintenance treatment.

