6. N/A
7. Adverse events will be graded using the Common Terminology Criteria for Adverse Events (CTCAE).
8. The study will be conducted in compliance with regulatory requirements and Good Clinical Practice. Quality control will be applied to each stage of data handling to ensure that data are accurate, reliable and processed correctly.
9. Should a temporary or permanent suspension of our study occur, the occurrence will be reported to the PPHS, sponsor, and IRB.

Part II. Data Monitoring Committee/Data Safety Monitoring Board (DMC/DSMB)

N/A

e) Withdrawal of Subjects

When an individual who has signed the ICF is not enrolled in the study or withdraws/is withdrawn prior to completing the study, the reason is to be documented on the Discontinuation/Completion Form (or equivalent) and in the final study report. Reasons for subject withdrawal may include:

 Mount Sinai	Protocol Name:	A double-blinded, placebo-controlled study to evaluate the tolerability and efficacy of Enstilar® (calcipotriene and betamethasone dipropionate) Foam in the treatment of chronic plaque psoriasis in patients with skin of color (Fitzpatrick skin phototypes IV-VI).
	Principal Investigator:	[name], MPH
	Primary Contact Name/Contact Info:	[name], MPH [contact]
	Date Revised:	08/10/2017
	Study Number:	IF2166478

- Not enrolled (e.g. fails to meet inclusion/exclusion criteria, chooses not to enroll, etc.)
- Participant is determined to be ineligible after enrollment
- Subject's choice to withdraw
- Investigator terminated (e.g. noncompliance, etc.)
- Adverse Event
- Lost to follow-up
- Other

Subjects may withdraw from the trial at any time at their request, or they may be withdrawn at any time at the discretion of the Sponsor, PI, or designee for safety, behavioral, or administrative reasons. Subjects may be withdrawn from this study without their consent if the research study is being stopped; or if the instructions of the study team have not been followed.

If a subject does not return for a scheduled visit, *three documented attempts will be made to contact the subject in order to establish the reason for withdrawal, and the outcome will be documented.* The PI or designee should inquire about the reason for withdrawal, request that the subject return for a final visit, if applicable, and follow-up with the subject regarding any unresolved adverse events.

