Should a subject withdraw from the trial and also withdraw consent for disclosure of future information, no further evaluations should be performed and no additional data should be collected. The PI and staff may retain and continue to use any data collected before such withdrawal of consent. Removed or withdrawn subjects will not be replaced.

If a subject fails to report to the test facility for a scheduled visit and cannot be rescheduled within the permitted window of time (as applicable), the Site should consult with the Sponsor to determine if the subject should be documented as having withdrawn/dropped from the study.

2) Risks to Subjects

The following list of side effects is the ones that may be associated with the use of Enstilar® foam:

Observed in less than 1% of subjects (based on clinical trials):

- Application site reactions:
 - Irritation
 - Pruritus
- Folliculitis
- Skin hypopigmentation

 Mount Sinai	Protocol Name:	A double-blinded, placebo-controlled study to evaluate the tolerability and efficacy of Enstilar® (calcipotriene and betamethasone dipropionate) Foam in the treatment of chronic plaque psoriasis in patients with skin of color (Fitzpatrick skin phototypes IV-VI).
	Principal Investigator:	[name], MPH
	Primary Contact Name/Contact Info:	[name], MPH [contact]
	Date Revised:	08/10/2017
	Study Number:	IF2166478

- Hypercalcemia
- Urticaria
- Exacerbation of psoriasis

Observed uncommon adverse reactions (based on post-marketing data):

- Atrophy of thin skin
- Telangiectasia of the skin
- Dryness of the skin
- Perioral dermatitis
- Secondary infections of the skin
- Miliaria

Other warnings:

- **Hypercalcemia and hypercalciuria** – Hypercalcemia and hypercalciuria have been observed with the use of Enstilar® foam. If either of these conditions develop, Enstilar® should be discontinued until calcium levels normalize in the blood and/or urine.
- **Endocrine system effects** – The systemic absorption of topical corticosteroids may lead to reversible suppression of the hypothalamic-pituitary-adrenal (HPA) axis, which may result in clinical glucocorticoid insufficiency either during treatment or upon withdrawal of the topical steroid. The risk of HPA axis suppression is higher with use of high-potency steroids, treatment of a large surface area, prolonged use, use of occlusive dressings, altered skin barrier, liver failure, and young age.

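### The stated 25 completers are reached only with zero dropout, because 25 are randomized, nobody is replaced and withdrawal is provided for

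*Protocol*

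**What the plan says.** The opening summary of the protocol gives 25 as the number of subjects who "are expected to complete this study, which will run for a total of up to 12 weeks". It then splits them by arm: "a total of 20 subjects will be randomized to Enstilar® and a total of 5 subjects will be randomized to vehicle". Section 5 c), Number of Subjects, says that patients "will be screened with a goal of 25 total subjects randomized" and goes straight on to "All 25 randomized subjects are expected to complete all study procedures". The procedures section gives the same allocation as a ratio: "Subjects will be randomized in a 4:1 ratio to Enstilar® or placebo, respectively".

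The section on Withdrawal of Subjects closes the route by which a lost subject could be made good: "Removed or withdrawn subjects will not be replaced".

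The same protocol plans for people leaving. "Subjects may withdraw from the trial at any time at their request" is followed by removal at the discretion of the sponsor or investigator. The listed reasons include adverse event, noncompliance, loss to follow-up and ineligibility found after enrolment. The procedures section describes a final visit for early leavers, Study Timelines gives the Week 8 visit a second use as the discontinuation visit, and Payments to Subjects provides part payment for those who do not finish.

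**The concern.** One number, 25, serves both as the number randomized and as the number completing. With no replacement, the two can coincide only if no randomized subject is lost. A protocol that sets out how withdrawals are documented, followed up and paid for gives no ground for expecting none.

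This matters because 25 (20 and 5) is the only size figure in the document. A reader will use it to judge how much information the blinded comparison with vehicle can carry. The control arm has five subjects, so one missing vehicle outcome is a fifth of that arm.

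**Working it through.** **Inputs from the protocol.** Randomized: 25. Expected to complete: 25. Arms: 20 Enstilar and 5 vehicle. Replacement: none. Time at risk after randomization: 8 weeks, since Study Timelines makes up the 12 weeks from a screening period of up to 4 weeks plus 8 weeks enrolled, and randomization takes place at Baseline. Primary endpoint: IGA treatment success at Week 4. Completion: Week 8.

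**Inputs not in the protocol.** The loss rate d. I take 2%, 5%, 10% and 15% over the 8 weeks, independent between subjects, as an assumed range.

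**Step 1: the plan's own figure.** 25 × 4/5 = 20 and 25 × 1/5 = 5, so the split reproduces. The number needed to expect 25 completers is 25/(1 − d), which equals 25 only at d = 0.

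**Step 2: what follows at other loss rates.** Chance that all 25 complete: (1 − d)^25. Expected completers: 25(1 − d). Chance that all five vehicle subjects complete: (1 − d)^5. For Week 4 I add one further assumption, that loss is spread evenly in hazard over the 8 weeks. The expected number still in the study at Week 4 is then 25 × √(1 − d).

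| Assumed loss d | All 25 complete | Expected completers (Week 8) | Expected still in at Week 4 | All 5 vehicle subjects complete |
|---|---|---|---|---|
| 2% | 60% | 24.5 | 24.7 | 90% |
| 5% | 28% | 23.8 | 24.4 | 77% |
| 10% | 7% | 22.5 | 23.7 | 59% |
| 15% | 2% | 21.3 | 23.0 | 44% |

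The last column concerns completion to Week 8. It is not the chance of an intact vehicle arm at Week 4, which would be higher.

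**Step 3: which arm is sensitive.** For a difference between two arms, the sample-size part of the variance is 1/n1 + 1/n2.

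- 20:5 gives 1/20 + 1/5 = 0.250.
- 19:5 gives 1/19 + 1/5 = 0.253, a rise of about 1% (standard error +0.5%).
- 20:4 gives 1/20 + 1/4 = 0.300, a rise of 20% (standard error +9.5%).
- 10:5 gives 1/10 + 1/5 = 0.300.

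If the subject is excluded from the comparison, losing one vehicle subject therefore costs as much on this factor as losing 10 of the 20 active subjects.

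**The case against.** The strongest reply is that nothing here is an arithmetic error or a contradiction. 20 + 5 = 25, the ratio is 4:1, and both statements about completion are worded as expectations. That stands. A reader might infer that the design fails to deliver its stated size, but the documents do not support this: delivery depends on a dropout rate that they do not give. What they support is that the figure holds only at zero loss.

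Three further limits also stand.

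- **Time at risk.** It is 8 weeks, not 12. Those who fail screening are screening failures, not lost randomized subjects.
- **Completion is not the primary endpoint.** A subject lost between Week 4 and Week 8 is a non-completer with a primary outcome. Early leavers are also asked back for the Visit 6 procedures, which by Table 1 include the IGA, so leaving does not always mean having no assessment.
- **Power.** A reader might infer that one vehicle dropout breaks the power of the primary comparison. The protocol states no alpha, power, effect size or analysis set, so no promised power can be missed, and the effect depends on how a missing outcome is handled. As illustration only, take assumed success of 50% v 10% and a two-sided 5% Fisher test. Power is 25.0% at 20:5 and 8.7% at 20:4 if the vehicle subject is excluded, but the rejection probability is 27.6% if that subject is kept and counted as a failure. The exact test is also coarse at this size: 19:4 gives 11.9%, more than 20:4. At 70% v 10% the fall from 20:5 to 20:4 is from 70% to 54%. These figures are too dependent on assumptions to be part of the finding.

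The objection does not touch the statement of size itself. The number randomized, the number expected to complete and the replacement rule are all fixed in the protocol, so this is not a matter left to the analysis plan.

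**Conclusion.** The point holds as a correction to a stated size. The protocol's 25 completers are reached only if none of the 25 randomized subjects leaves in the 8 weeks after randomization. At an assumed loss of 5% to 15% the chance of that is 28% down to 2%, and about 21 to 24 completers are to be expected. Even at 2% loss the chance is only 60%. These percentages rest on the assumed rates and on independence; that zero loss is required rests on the text alone.

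The greater sensitivity of the vehicle arm (0.300 against 0.253 from a base of 0.250) applies if a subject without a Week 4 outcome is excluded. It says nothing about losses after Week 4.

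**What to change.** In the opening summary and in Number of Subjects, state 25 as the number randomized (20 to Enstilar, 5 to vehicle) and say there that withdrawn subjects are not replaced. Delete the sentence "All 25 randomized subjects are expected to complete all study procedures". In its place give the expected number of completers under a loss assumption that the site states and can support from its own experience, separately for Week 4 (primary endpoint) and Week 8 (completion). At 5% to 15% loss the Week 8 figure would read about 21 to 24; that range is an example and should not be copied in without a basis.

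The cost is a few sentences. Enrolment, allocation and the replacement rule stay as they are. The only downside is a slightly less favourable stated number of completers.
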